Effects of Low-Flow Anesthesia on Hemodynamic Parameters and Oxygenation in Morbidly Obese Patients Undergoing Bariatric Surgery: A Prospective, Randomized Clinical Trial

***[name]**, Asst. [name] of Anesthesiology and Reanimation, Inonu University Medical Faculty, Malatya, Turkey

[name], Asst. [name] of Anesthesiology and Reanimation, Inonu University Medical Faculty, Malatya, Turkey

[name], Postgraduate student. Department of Anesthesiology and Reanimation, Inonu University Medical Faculty, Malatya, Turkey

Address all correspondence to:

[name], Asst. [name] of Anesthesiology and Reanimation, Inonu University Medical Faculty, Malatya, Turkey

Mail: [contact]

[contact]

[contact]

A short title: **Effects of Low-Flow Anesthesia in Morbidly Obese Patients**

Conflict of Interest:

The authors declare that they have no conflict of interest.

Funding Information:

None

Study Protocol

Morbidly obese patients with American Society of Anesthesiology (ASA) scores of III-IV, who were aged 18–65 years old, and had a BMI >40 were included in our study. Patients were interviewed before surgery to obtain informed consent. Patients were excluded if they were pregnant or had uncontrolled diabetes mellitus, cardiovascular disease, pulmonary disease, cerebrovascular disease, or drug and alcohol addiction. Patients who refused informed consent were also excluded.

Patients were taken to the operating room without premedication. Standard monitoring procedures were used, including heart rate (HR), noninvasive blood pressure (NIBP), electrocardiogram (ECG), peripheral oxygen saturation (SpO_2), and body temperature. A general anesthesia protocol was administered in all patients by an experienced anesthesiologist. After preoxygenation (100% 4 L/min O_2 for 5 min), propofol (1–2 $\text{mg} \cdot \text{kg}^{-1}$), rocuronium (0.8–1 $\text{mg} \cdot \text{kg}^{-1}$) and fentanyl (0.1 $\mu \text{g} \cdot \text{kg}^{-1}$) were administered during the induction of anesthesia via intravenous (IV) route at doses calculated according to ideal body weights. Randomization was performed with the MedCalc for Windows (medcalc.com.tr.), version 16 statistical software. Forty-eight patients were randomly allocated to two study groups: a low-flow group (Group L, $n = 24$) and a normal-flow group (Group N, $n = 24$). Patients in Group L received a fresh gas flow of 4 L/min for the first 10 minutes and were then maintained with a fresh gas flow of 0.75 L/min. Patients in Group N received the same initial fresh gas flow of 4 L/min for the first 10 minutes but were then maintained with a fresh gas flow of 1.5 L/min. All patients were mechanically ventilated with a tidal volume of 8 mL/kg based on ideal body weight and a frequency of 12–16 breaths/min using a Dräger Primus ventilator (Dräger AG, Lübeck, Germany). End-tidal carbon dioxide (EtCO_2) was continuously monitored after intubation. Tidal volume and ventilation rate were adjusted to maintain EtCO_2 partial pressure

of arterial blood at 35–45 mmHg. Rocuronium was intermittently injected according to need based on Train of Four (TOF; Dräger AG, Lübeck, Germany) values. TOF responses were assessed by ulnar nerve stimulation and adductor muscle response. Anesthesia was maintained in both groups at desflurane inhalation in a 0.5 O₂ oxygen-air mixture. Desflurane was discontinued with the beginning of the skin sutures and the fresh gas flow was changed to 4 L/min of oxygen for both groups. In patients who did not experience complications during the surgery, sugammadex (IV, 2–4 mg/kg, Bridion®, MSD, Greenville, USA) was then administrated to reverse residual muscle relaxation at the end of surgery. All patients received the standard surgical procedures determined by the same team of surgeons with experience in gastroenterology surgery. Pneumoperitoneum pressure ranged between 10 – 12 mmHg. Surgical management of sleeve gastrectomy was not changed in any way. In all patients, postoperative analgesia was achieved IV analgesic medication using appropriate doses of tramadol (0.5-1 mg/kg, IV) and paracetamol (1 gr, IV) at the time of beginning skin sutures (16).

Hemodynamic parameters such as HR, SpO₂, EtCO₂, MAP and values of arterial blood gas were recorded before anesthesia (T₀), 5 min before insufflation of CO₂ (T₁) and 15 min after awakening from anesthesia (T₂). In addition to anesthesia and surgery times, perioperative and postoperative complications were recorded.

Statistical Analysis Plan

Using the power calculation method (OpenEpi, Version 3), assuming an alpha of 0.05 and a beta of 0.80, we calculated that 22 patients per group should be included in this study. Data were analyzed using the Statistical Package for the Social Sciences program (SPSS 22.0). As some pre and anesthetic characteristics of patients were distributed abnormally nonparametric statistics was used. Quantitative data are presented as mean or standard deviation and categorical data are shown as numbers or percentages. Continuous variables were compared between the groups using Mann-Whitney U-test. Categorical variables were summarized using frequencies and percentages (%) and compared between the groups using Chi-Squared Test. The results were evaluated at a 95% confidence interval at a significance level of $p<0.05$.

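### At most one of the three scheduled readings (T1) falls while gas flows differ, exposure at T1 is unknown, and no reading is scheduled from T1 to skin suturing

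*Combined protocol and SAP*

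**What the plan says.** All of this is in the Study Protocol section unless noted.

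- **Flows.** Group L received "4 L/min for the first 10 minutes and were then maintained with a fresh gas flow of 0.75 L/min". Group N had the same opening phase "but were then maintained with a fresh gas flow of 1.5 L/min". The event that starts the 10 minutes is not named. Preoxygenation also runs at 4 L/min: "After preoxygenation (100% 4 L/min O_2 for 5 min".
- **End of the difference.** "Desflurane was discontinued with the beginning of the skin sutures", and at that moment both groups go to 4 L/min of oxygen.
- **Scheduled readings.** Heart rate, SpO₂, EtCO₂, MAP and arterial blood gas are "recorded before anesthesia (T₀), 5 min before insufflation of CO₂ (T₁) and 15 min after awakening from anesthesia (T₂".
- **Other records.** Anesthesia and surgery times are recorded, as are perioperative and postoperative complications. The times of flow change, insufflation and T1 are not listed.
- **Monitoring for care.** "Standard monitoring procedures were used, including heart rate (HR), noninvasive blood pressure (NIBP", with SpO₂ also on the list. "End-tidal carbon dioxide (EtCO_2) was continuously monitored after intubation".
- **Analysis.** The Statistical Analysis Plan compares continuous variables between groups with the Mann-Whitney U-test. It has no term for time on the assigned flow.

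**The concern.** The title asks what low-flow anesthesia does to hemodynamic parameters and oxygenation. A randomized comparison answers that most directly with readings taken while the two flows are in force. Here the period of differing flow is bounded by events (flow change and start of skin suturing), while the readings are tied to other events (start of anesthesia, insufflation and awakening). Two things follow.

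First, T1 is the only reading that can fall inside the period, and nothing fixes how far inside. If the groups look alike at T1, a reader cannot tell whether the flows made no difference or had differed for only a few minutes.

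Second, everything from T1 to skin suturing has no scheduled between-group data on these variables. That stretch includes the whole interval from insufflation to skin suturing. Neither a different test nor a larger sample can supply data that were not scheduled.

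**Working it through.** The plan's one calculated figure, 22 patients per group, does not bear on timing. No effect size or SD is given, so it cannot be reproduced, and nothing below depends on it.

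**Step 1. Place each reading against the period of differing flow** (minute 10 to the start of skin suturing).

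| Reading | Timing | While flows differ? |
|---|---|---|
| T0 | Before anesthesia | No |
| T1 | 5 min before insufflation | Only if more than 10 min after the flow clock starts |
| T2 | 15 min after awakening | No; both arms returned to 4 L/min at skin suturing |

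At most 1 of 3 falls in the period. Between insufflation and skin suturing the count is 0 of 3. Neither count needs an assumption.

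**Step 2. Exposure at T1.** Let I be minutes from the start of the 10-minute phase to insufflation. T1 is at I − 5 and the flow change at 10, so

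exposure = max(0, (I − 5) − 10) = max(0, I − 15).

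I is not in the documents. For assumed values:

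| I (min, assumed) | T1 at (min) | Exposure (min) |
|---|---|---|
| 15 | 10 | 0 |
| 20 | 15 | 5 |
| 25 | 20 | 10 |
| 30 | 25 | 15 |
| 40 | 35 | 25 |

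Ten minutes of exposure needs I of at least 25 min.

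**Step 3. The undefined start.** Let X be minutes from the end of preoxygenation to insufflation.

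- Clock starts with the 5-min preoxygenation: I = X + 5, exposure max(0, X − 10).
- Clock starts when preoxygenation ends: I = X, exposure max(0, X − 15).
- Clock starts at induction or intubation, D min after preoxygenation ends: I = X − D, exposure max(0, X − D − 15).

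Where exposure is above zero under each reading, the first two differ by 5 min, and the first and third by 5 + D min. Five minutes is therefore not a bound on the ambiguity.

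**Step 4. Time without a reading.** Let S be minutes from insufflation to skin suturing (also not stated). The time from T1 to skin suturing is S + 5. Of this, all is differing-flow time when I is at least 15. For assumed S of 60 to 120 min, that is 65 to 125 min. The differing-flow period is I + S − 10. With I of 15 to 40 min, the share elapsed by T1 runs from 0% (I = 15) to 25/90 = 28% (I = 40, S = 60).

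**The case against.** **T1 and T2 are deliberate choices.** T1 avoids the effects of pneumoperitoneum. T2 follows the whole low-flow exposure and includes arterial blood gas, so it is direct though delayed evidence on oxygenation. This stands. Both readings should be kept, and both comparisons are valid for what they measure.

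**The interval is not empty.** Patients are monitored throughout and perioperative complications are recorded. That is true, but monitoring for care is not a scheduled between-group reading. Recorded complications cover the interval only coarsely and do not describe MAP or SpO₂.

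**No objective about the course of maintenance is stated.** Also true: the question is taken from the title. The gap therefore limits what may be concluded and does not breach a stated objective.

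**The exposures are assumed.** They are, and anesthesia and surgery times might partly bound them if kept as clock times. The counts in Step 1 do not depend on them.

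**The text is in the past tense**, so a new reading may no longer be possible. This stands, and the fix allows for it.

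Two stronger readings are tempting. A reader might infer that T1 was taken before flows differed, so that no reading tests the intervention. That needs I of 15 min or less, and the documents do not give I. A reader might also infer that the trial can conclude nothing about hemodynamics or oxygenation. That goes too far, because T1 and T2 remain usable.

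**Conclusion.** The point holds as a limit on coverage and interpretation. At most one of three scheduled readings falls while the randomized flows differ, and none falls between insufflation and skin suturing. Exposure at T1 is max(0, I − 15) min. Since I, the event that starts the 10 minutes, and the relevant clock times are all unstated, that exposure could be long, short or zero.

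The schedule cannot support a conclusion, in either direction, about hemodynamics or oxygenation from T1 to skin suturing. It can support a pre-insufflation comparison at T1 and a carry-over comparison at T2. No effect size or direction of bias is claimed. The counts rest on the text alone; the minute values and shares rest on assumed I and S. This should be fixed, but it does not invalidate the trial.

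**What to change.** Keep T0, T1 and T2.

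- **Add one reading.** Take heart rate, MAP, SpO₂ and EtCO₂ from the existing monitors immediately before desflurane is discontinued and flow goes to 4 L/min. Under the plan as written, this point always falls after insufflation and while flows differ. A set time after the flow change would not guarantee that, because I is unknown.
- **Make exposure reportable.** State the event that starts the 10 minutes. Record the clock times of flow change, insufflation, T1 and the new reading.
- **Record context.** Note whether pneumoperitoneum is present, since the text does not say when CO₂ is released. Record tidal volume and rate, because EtCO₂ is steered: "Tidal volume and ventilation rate were adjusted to maintain EtCO_2 partial pressure" within 35–45 mmHg.
- **Analysis.** Compare groups at the new point with the planned Mann-Whitney test, as a supporting and not a main comparison.

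**Cost.** Per patient: 4 values + 4 times + 1 flag + 2 ventilation settings = 11 items, or 11 × 48 = 528 in all, with no extra arterial sample. The four added tests at p < 0.05 bring 4 × 0.05 = 0.20 expected false positives if there is no effect, in a plan that states no multiplicity control. Exposure at the new point varies with length of surgery, which is why its time must be recorded. The reading informs SpO₂ and hemodynamics, not arterial oxygenation.

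**If data collection is complete.** The reading can be added only if monitor records were stored. Otherwise, report time from flow change to T1 where records allow, and limit hemodynamic and oxygenation conclusions to the pre-insufflation and post-emergence time points.

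### The SAP names only the unadjusted Mann-Whitney test for outcomes measured at T0, so precision is lost wherever T0 and follow-up correlate

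*Combined protocol and SAP*

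**What the plan says.** The last paragraph of the Study Protocol section lists heart rate, SpO2, EtCO2, MAP and arterial blood gases, and states that "values of arterial blood gas were recorded before anesthesia (T₀"), with repeat measurements at T1 (before CO2 insufflation) and T2 (after awakening). It adds: "In addition to anesthesia and surgery times, perioperative and postoperative complications were recorded".

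On continuous data, the Statistical Analysis Plan gives one method: "Continuous variables were compared between the groups using Mann-Whitney U-test". It mentions no covariate adjustment, change from T0 or repeated-measures model. The reason given for nonparametric methods is that some patient characteristics were not normally distributed; the outcomes are not named specifically. Categorical variables go to a chi-squared test.

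EtCO2 is listed with the T0 measurements, but the ventilation text says it "was continuously monitored after intubation", so whether a T0 value exists is unclear.

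**The concern.** Both groups receive the same fresh gas flow for the first 10 minutes, and T0 precedes anesthesia. T0 is therefore a true pre-treatment covariate, measured on the same variable as the outcome. A two-sample rank test at T1 or T2 leaves between-patient variation that T0 could explain in the error term.

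Randomisation keeps the test valid, so neither bias nor type I error is at issue. With 24 patients per arm, though, a real difference is more likely to be missed than the collected data require, and a finding of no difference rules out less. That matters if low flow is to be reported as similar to normal flow.

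The point covers heart rate, MAP, SpO2 and arterial blood gases. It does not cover complications (chi-squared), anesthesia and surgery times (no T0 value), or EtCO2 unless a T0 value is confirmed.

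**Working it through.** **Inputs from the documents.** 48 randomised, 24 per arm; sample-size statement: "assuming an alpha of 0.05 and a beta of 0.80, we calculated that 22 patients per group should be included in this study".

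**Assumptions.** Two-sided testing; the stated beta of 0.80 read as 80% power; rho from 0 to 0.7; a difference of 0.6 SD or 0.845 SD. The documents give no effect size, SD, sizing endpoint or rho.

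**The plan's own figure.** The 22 per group cannot be reproduced without an effect size and SD. Solved backwards, the implied standardised difference is (1.960 + 0.842) × √(2/22) = 0.845. Hence the second effect size.

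**Interval width.** Adjusting for T0 multiplies the error variance by 1 − rho². The half-width of a 95% CI for a mean difference, in SD units, is t × √(2/24) × √(1 − rho²):

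- unadjusted: 0.581
- rho 0.2: 0.570
- rho 0.5: 0.504
- rho 0.7: 0.415

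The equivalent unadjusted sample size per arm is 24/(1 − rho²): 24/0.96 = 25, 24/0.75 = 32 and 24/0.51 = 47. Allowing for estimation of the covariate slope, simulation puts these at about 24.5, 31 and 46.

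**Power by simulation.** 24 per arm, normal data, two-sided 0.05, 10,000 replicates per cell (Monte Carlo standard error at most √(0.25/10,000) = 0.5 points):

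| Difference | rho | Mann-Whitney | Mann-Whitney on change | rank-ANCOVA | ANCOVA |
|---|---|---|---|---|---|
| 0.6 SD | 0 | 50.8% | 28.2% | 50.9% | 52.3% |
| 0.6 SD | 0.2 | 50.3% | 34.3% | 52.5% | 54.0% |
| 0.6 SD | 0.5 | 50.7% | 50.6% | 61.8% | 64.7% |
| 0.6 SD | 0.7 | 51.0% | 72.0% | 75.7% | 80.6% |
| 0.845 SD | 0.2 | 79.8% | 59.4% | 81.0% | 82.9% |
| 0.845 SD | 0.5 | 79.4% | 79.5% | 88.0% | 90.6% |
| 0.845 SD | 0.7 | 79.5% | 94.9% | 96.5% | 97.9% |

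A separate run of 20,000 replicates at 0.845 SD agrees. Mann-Whitney stays at about 79% throughout; rank-ANCOVA to ANCOVA gives 88-91% at rho 0.5 and 96-98% at rho 0.7.

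**Non-normal data, difference 0.6 SD.** Strong skew (log-normal, log-SD 1.0):

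| rho | Mann-Whitney | raw ANCOVA | rank-ANCOVA | log ANCOVA |
|---|---|---|---|---|
| 0.2 | 50.3% | 36.9% | 51.7% | 53.5% |
| 0.5 | 50.4% | 43.7% | 60.3% | 64.1% |
| 0.7 | 50.6% | 55.8% | 76.0% | 80.6% |

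For SpO2-like integers capped at 100 (assumed latent mean 99, SD 2), Mann-Whitney against rank-ANCOVA is 47.6% vs 48.8%, 48.2% vs 56.1% and 48.2% vs 68.7% at rho 0.2, 0.5 and 0.7.

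**Type I error.** Null rejection was 4.5-5.7% for Mann-Whitney, rank-ANCOVA and log-scale ANCOVA, and 3.3-4.2% for raw ANCOVA under the strong skew.

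**The case against.** The planned test is valid, and the whole loss rests on a correlation that the documents do not report. That correlation may be low for more than CO2 at T1, where ventilation is adjusted to a target. Inspired oxygen is set by protocol at T1, both arms are switched to oxygen before T2, and SpO2 has a ceiling, so oxygenation outcomes may also track T0 weakly. At rho 0.2 the gain is one or two points of power. This stands as a limit on size. It does not argue against adjusting, because adjustment costs almost nothing: at rho 0, power is unchanged and the adjusted interval is only about 1% wider.

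Four further points stand in part:

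- Some of the advantage of ANCOVA over Mann-Whitney is parametric efficiency under normal data (52.3% against 50.8% at rho 0). The like-for-like comparison is rank-ANCOVA, which still gains 61.8 − 50.7 = 11.1 points at rho 0.5 and 0.6 SD.
- Mann-Whitney on change from T0 recovers most of the loss at rho 0.7. It recovers none at 0.5, does harm below that, and is not written in the plan.
- Where rank-ANCOVA is used, the accompanying shift estimate has an unadjusted interval. Only the test gains.
- The documents do not say that T1 falls after the flows diverge, and both arms return to the same flow before T2. Precision helps little where the arms have barely differed.

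Non-normality is a reason to choose the scale carefully, not to leave T0 out: rank or log-scale ANCOVA keeps the gain under strong skew.

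**Conclusion.** The concern holds. T0 values are collected for the named outcomes, and the plan gives them no role in the only test it names for continuous data. The consequence is a conditional loss of efficiency with type I error intact: nil at rho 0, small at 0.2, and material from about 0.5. At 0.6 SD and rho 0.5, about 51% power could be 62-65%, and the interval narrows from 0.58 to 0.50 SD.

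These figures assume 24 analysed per arm, two-sided testing at 0.05, normal data, and the stated rho and effect sizes, neither of which is in the documents. The 0.845 SD case also assumes that 80% power was meant. The change should be made, but the existing comparisons are not wrong without it.

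**What to change.** Compare the groups at T1 and at T2 by ANCOVA with the outcome's own T0 value as covariate. Fix the scale for each outcome in advance, not from residuals. For example, use the raw scale for heart rate and MAP, the log scale for arterial partial pressures, and rank-ANCOVA for SpO2 and any outcome whose scale cannot be justified beforehand. Raw-scale ANCOVA should not be the default for strongly skewed outcomes, where it can do worse than Mann-Whitney.

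Report the adjusted difference, or the ratio on the log scale, with its 95% CI. With rank-ANCOVA, give medians (IQR) and a Hodges-Lehmann shift with 95% CI, labelled unadjusted. Keep Mann-Whitney as a sensitivity analysis, and as the test for anesthesia and surgery times and for EtCO2 unless a T0 value is confirmed.

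The cost is a few lines of SAP text. No new data are needed, and the SPSS package already named can run the analysis. The SAP is written in the past tense ("Data were analyzed using the Statistical Package for the Social Sciences program (SPSS 22.0")). If the analysis is complete, add the adjusted results beside the Mann-Whitney results and label them post hoc.

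### No primary outcome or time point is named and every result is judged at p<0.05, so the plan does not fix which result carries the conclusion

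*Combined protocol and SAP*

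**What the plan says.** The last paragraph of the Study Protocol lists the measurements and the baseline time: "Hemodynamic parameters such as HR, SpO₂, EtCO₂, MAP and values of arterial blood gas were recorded before anesthesia (T₀"). Two later times follow in the same sentence, one during anesthesia and one in recovery: "5 min before insufflation of CO₂ (T₁) and 15 min after awakening from anesthesia (T₂"). The blood gas values are not enumerated. Anesthesia and surgery times and complications are recorded as well, and no rank is given to any of these.

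The Statistical Analysis Plan gives one rule for continuous outcomes, "Continuous variables were compared between the groups using Mann-Whitney U-test", and a chi-squared test for categorical ones. One threshold covers them all: "The results were evaluated at a 95% confidence interval at a significance level of" p<0.05. The sample-size statement reads "assuming an alpha of 0.05 and a beta of 0.80, we calculated that 22 patients per group should be included in this study". It attaches no outcome, difference, SD or rate to that number.

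Neither section contains a primary outcome, a primary time, a hypothesis, a testing order or a multiplicity rule.

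**The concern.** A reader needs to know in advance which comparison decides whether low flow differs from normal flow. Two indirect sources might have supplied it, and neither does. The title names two broad domains, hemodynamics and oxygenation, rather than an endpoint. The sample-size sentence names no outcome.

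Two things are at stake. First, the result that carries the conclusion can be picked after the data are seen. Second, a conclusion that may rest on any one of several tests does not have the 5% error rate that each single test has.

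**Working it through.** **The plan's own figure.** The 22 per group cannot be rebuilt, because no effect is stated. Solving d = (z_α + z_power) × √(2/n) for n = 22, where √(2/22) = 0.3015, gives:

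- two-sided 0.05, 0.80 read as power: (1.960 + 0.842) × 0.3015 = 0.845 SD
- one-sided 0.05, 0.80 read as power: (1.645 + 0.842) × 0.3015 = 0.750 SD
- two-sided 0.05, beta literally 0.80 (power 0.20): (1.960 − 0.842) × 0.3015 = 0.337 SD

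None of these appears in the plan, so the sample size does not reveal an intended primary.

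**Counting tests.** The four named variables at the two times after baseline give 4 × 2 = 8 tests. T0 is a baseline and is not counted. The blood gas values would add tests, but their number is not given, so no figure is claimed for them. Two smaller counts are shown: 7 tests if EtCO₂ were not available at T2, and 4 tests if only T2 were tested.

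**Chance of at least one p<0.05 when flow has no effect.** If independent, this is 1 − 0.95^m:

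- m = 8: 1 − 0.6634 = 0.337
- m = 7: 1 − 0.6983 = 0.302
- m = 4: 1 − 0.8145 = 0.185

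For correlated tests I took normal statistics with one common correlation r and two-sided 0.05, by numerical integration. The values of r are assumptions.

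| Tests | independent | r = 0.5 | r = 0.7 | r = 0.9 |
|---|---|---|---|---|
| 8 (four variables, T1 and T2) | 34% | 25% | 19% | 12% |
| 7 (EtCO₂ not available at T2) | 30% | 23% | 18% | 11% |
| 4 (T2 only) | 19% | 16% | 13% | 9% |

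**Check with the planned test.** Simulated Mann-Whitney tests with 24 against 24 patients (20,000 replicates) gave 0.327, 0.254, 0.190 and 0.126 for 8 tests, and 0.182, 0.158, 0.129 and 0.099 for 4 tests, in the same order of correlation. A single test rejected in 0.047 to 0.051 of runs, so each test on its own holds about 5%.

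**The case against.** The strongest reply is that these percentages presuppose a decision rule the plan never states. It sets a threshold for each test and makes no confirmatory claim. In a 48-patient study of several physiological measures, unadjusted testing read as exploratory is defensible. That stands. A reader might infer that this trial has a 34% false-positive rate, or that a multiplicity adjustment is mandatory, and the documents support neither. The 34% also needs independence, which is unlikely for repeated values in the same patients. A single common correlation across different measures is a convenience. What the reply does not remove is the omission itself: nothing is labelled exploratory, and nothing is labelled primary.

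Three further readings are tempting.

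- *T1 can be left out because the groups may hardly differ by then.* Group N "received the same initial fresh gas flow of 4 L/min for the first 10 minutes" as Group L, and T1 is tied to CO₂ insufflation, so exposure to different flows before T1 is not shown. But it is not ruled out either, and informativeness concerns power. A test at an uninformative time still rejects about 5% of the time. The 4-test row applies only if T1 is not tested, which the plan does not say.
- *EtCO₂ cannot exist at T2.* The protocol says it "was continuously monitored after intubation", which does not show that it is missing after awakening, and the measurement list includes it at T2. The 7-test row is a what-if.
- *The authors chose their result after seeing the data.* The analysis section is in the past tense, including its sentence on group comparisons. This suggests that the comparisons are done but does not prove it, and nothing shows selection. The remark on non-normality concerns patient characteristics, not outcomes.

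**Conclusion.** The omission is real and must be fixed before any result is presented as confirmatory. The plan fixes neither the outcome nor the time that carries the conclusion, and its sample size does not supply one. The lack of multiplicity control matters because no primary is named; with one primary, no adjustment would be needed for the main conclusion.

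If any one significant result were read as the effect of low flow, the chance of a false positive would exceed 5% in every case computed: 12% to 34% for 8 tests, 11% to 30% for 7, and 9% to 19% for 4. This rests on that decision rule, on two-sided tests at 0.05, on the four named variables only, and on assumed correlations from 0 to 0.9. The figures illustrate the consequence and do not estimate this trial's error rate.

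**What to change.** **If outcomes have already been compared by group**, as the past tense suggests, do not name a primary now. State that none was prespecified, report every comparison made as an estimate with a 95% CI, and label all p-values exploratory. If an outcome underlay the 22 per group and this can be documented from before the comparison, identify it.

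*Cost:* one statement and a complete table of comparisons, with no added measurement. Unless such a documented primary exists, the trial makes no confirmatory claim.

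**If outcomes have not been compared**, first identify the outcome, difference and SD behind the 22 per group. Make that outcome, at one stated time (T1 or T2), the single primary, tested at two-sided 0.05. If there was none, choose one primary and one time and restate the sample-size sentence for it, saying whether 0.80 is power. Give a reason for the time, covering the shared initial flow before T1 and the fact that, before T2, "the fresh gas flow was changed to 4 L/min of oxygen for both groups". Report everything else as exploratory estimates with 95% CIs.

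*Cost:* one paragraph and a rewritten sample-size sentence, with no added measurement. A nominal p<0.05 on other variables no longer counts as a confirmed effect. The sample may also prove small for the chosen outcome: at 80% power and two-sided 0.05, 24 per group detects about 0.83 SD by t-test, or 0.826/√(3/π) = 0.85 SD by Mann-Whitney under normality.
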